#### 18.1.6. Overall Summary of Adverse Event

In addition to the summaries above, an overview of TEAEs will be summarized (not broken down by SOC or PT) by number and percentage of participants and by number of AEs:

- Any TEAEs
- Any related TEAEs\*
- Any serious TEAEs
- Any related serious TEAEs\*
- TEAEs leading to death
  - Liver related TEAEs leading to death
- TEAEs leading to study treatment discontinuation
  - Related TEAEs leading to study treatment discontinuation\*
  - Liver related TEAEs leading to study treatment discontinuation
- TEAEs leading to study treatment interruption (events recorded with an action taken with study treatment as "Drug interrupted" on the Adverse Events eCRF)
  - Related TEAEs leading to study treatment interruption\*
- TEAEs by maximum severity
- Related TEAEs by maximum severity\*
- TEAEs by maximum relationship to study treatment

\* "Related TEAEs" refers to TEAEs "related" or "probably related" to study treatment or are missing relationship.

Document: \quintiles.net\enterprise\Apps\sasdata\SASb\SAS\Arena\APD334\RZA28116\Biostatistics\Documenta

tion\SAP\503-Final SAP v2.0\APD334-203\_SAP\_Final v2.0-20231120\_clean.docx

Author: PPD Version Number: 2.0

Version Date: 20Nov2023

Template No.: CS\_TP\_BS016 Revision 7 Reference: CS\_WI\_BS005

Effective Date: 01Nov2021

Page 44 of 70

#### 18.2. Deaths

Information collected about deaths (eg., date of death, primary cause of death) will be presented in a data listing, as described in Section 18.1.4.

#### 18.3. Laboratory Evaluations

No local laboratory assessments will be used in any summaries except for lipid panel and thyroid panel tests. No local laboratory assessments will be used to derive maximum/minimum/worst value. Local laboratory assessments will be listed.

#### 18.3.1. Safety Laboratory Evaluations

Hematology, serum chemistry, coagulation, and urinalysis are analysed and reported by central laboratory and sometimes by local laboratory. Results out of reference range are flagged by the performing laboratory (eg, low, high). A full list of laboratory assessments to be included in the outputs is included in Clinical Study Protocol APD334-203 Table 6.

In general, presentations will use Système international d'Unités (SI units). Quantitative laboratory measurements reported as "< X" or "> X", where X may be the lower limit of quantitation (LLQ) or the upper limit of quantitation (ULQ), respectively, will be converted to X for the purpose of quantitative summaries, but will be presented as recorded, ie, as "< X" or "> X" in the listings. For urinalysis, only pH and specific gravity are considered as quantitative tests. If local and central laboratory assessments are available from the same day, central laboratory assessments will be used in the summary as per Section 6.4.

The following summaries will be provided for laboratory data:

- Value and change from Baseline by visit (for hematology, serum chemistry, quantitative urinalysis [pH and specific gravity], coagulation, and high-sensitivity C-reactive protein [hs-CRP])
- Incidence of abnormal values according to laboratory reference ranges by visit
- Incidence of lymphocytes  $< 0.2 \times 10^9/L$ ,  $0.5 \times 10^9/L$ , or neutrophils  $< 0.5 \times 10^9/L$ ,  $1 \times 10^9/L$  at end of treatment and anytime in the study
- Shift from end of treatment to each follow-up visit in incidence of lymphocytes in normal range and in incidence of lymphocytes of at least 80% percent of Baseline, by visit (2-Week Follow-Up, 4-Week Follow-Up, and Last Follow-Up)

Document: \\quintiles.net\enterprise\Apps\sasdata\SASb\SAS\Arena\APD334\RZA28116\Biostatistics\Documenta

tion\SAP\503-Final SAP v2.0\APD334-203 SAP Final v2.0-20231120 clean.docx

Version Number: 2.0 Author: PPD

> Version Date: 20Nov2023

Template No.: CS\_TP\_BS016 Revision 7 Reference: CS WI BS005

Effective Date: 01Nov2021

Page 45 of 70

- Shift from Baseline to end of treatment according to laboratory reference range (for quantitative measurements and categorical measurements)
- Evaluation of drug-induced serious hepatotoxicity (eDISH) plots for the following laboratory assessments (using values after the first administration of study treatment):
  - Maximum aspartate aminotransferase (AST) versus same-day total bilirubin
  - o Maximum alanine aminotransferase (ALT) versus same-day total bilirubin
  - Maximum gamma-glutamyl transferase (GGT) versus same-day total bilirubin
  - Maximum alkaline phosphatase (ALP) versus same-day total bilirubin

The eDISH plots above will be repeated with adjustment for elevated baseline.

- Incidence of hepatic enzyme elevations by visit
  - $\circ$  > 1 ×, 2 ×, 3 ×, 5 ×, 8 ×, 10 ×, 20 × upper limit of normal (ULN) elevation in ALT
  - >1 ×, 2 ×, 3 ×, 5 ×, 8 ×, 10 ×, 20 × ULN elevation in AST
  - > 3 ×, 5 ×, 10 ×, 20 × ULN elevation in either ALT or AST
  - o > 1 x, 1.5 x, 2 x, 3 x ULN elevation in total bilirubin
  - > 1 ×, 1.5 ×, 2 ×, 3 ×, 5 ×, 8 × ULN elevation in ALP
  - o > 1 ×, 2 ×, 3 ×, 5 ×, 8 × ULN elevation in GGT
  - > 3 × ULN elevation in either ALT or AST and > 1.5 × ULN elevation in total bilirubin
  - 3 × ULN elevation in either ALT or AST and > 2 × ULN elevation in total bilirubin
  - > 3 × ULN elevation in either ALT or AST and > 1.5 × ULN elevation in ALP
  - > 3 × ULN elevation in either ALT or AST in temporal association with treatment-emergent nausea, vomiting, anorexia, abdominal pain, or fatigue identified by PT, where temporal association is defined as ±14 days of onset date from the time of elevation.

If both central and local assessments of total bilirubin are available on the same day, the central result will take precedence over the local result in the eDISH plot. If the maximum AST, ALT, GGT, or ALP assessment occurs at 2 different dates, the assessment with the higher accompanying Bilirubin value will be used. Two versions of the eDISH plots will be presented, with one showing values as multiples of ULN, and the other one showing values as multiples of ULN, or subject's baseline, whichever is higher.

All laboratory tests will be listed. Subject's laboratory assessments at all timepoints will be listed in chronological order. Values outside of the laboratory reference range will be flagged. Values obtained from local laboratory will be flagged. Listing of lymphocytes and neutrophils over time in participants who ever had lymphocytes  $< 0.5 \times$ 

Document: \quintiles.net\enterprise\Apps\sasdata\SASb\SAS\Arena\APD334\RZA28116\Biostatistics\Documenta

tion\SAP\503-Final SAP v2.0\APD334-203 SAP Final v2.0-20231120 clean.docx

Author: PPD Version Number: 2.0

Version Date: 20Nov2023

Template No.: CS\_TP\_BS016 Revision 7 Reference: CS\_WI\_BS005

Effective Date: 01Nov2021

Page 46 of 70

109/L or neutrophils < 1 × 109/L will also be provided.

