16.6. APPENDIX 6: LIVER SAFETY: SUGGESTED ACTIONS AND FOLLOW-UP ASSESSMENTS

Potential Cases of Drug-Induced Liver Injury

Humans exposed to a drug who show no sign of liver injury (as determined by elevations in transaminases) are termed “tolerators,” while those who show transient liver injury but adapt are termed “adaptors.” In some participants, transaminase elevations are a harbinger of a more serious potential outcome. These participants fail to adapt and therefore are “susceptible” to progressive and serious liver injury, commonly referred to as DILI. Participants who experience a transaminase elevation above $3 \times$ ULN should be monitored more frequently to determine if they are “adaptors” or are “susceptible.”

In the majority of DILI cases, elevations in AST and/or ALT precede T bili elevations ($>2 \times$ ULN) by several days or weeks. The increase in T bili typically occurs while AST/ALT is/are still elevated above $3 \times$ ULN (ie, AST/ALT and T bili values will be elevated within the same laboratory sample). In rare instances, by the time T bili elevations are detected, AST/ALT values might have decreased. This occurrence is still regarded as a potential DILI. Therefore, abnormal elevations in either AST OR ALT in addition to T bili that meet the criteria outlined below are considered potential DILI (assessed per Hy’s law criteria) cases and should always be considered important medical events, even before all other possible causes of liver injury have been excluded.

The threshold of laboratory abnormalities for a potential DILI case depends on the participant’s individual baseline values and underlying conditions. Participants who present with the following laboratory abnormalities should be evaluated further as potential DILI (Hy’s law) cases to definitively determine the etiology of the abnormal laboratory values:

- Participants with AST/ALT and T bili baseline values within the normal range who subsequently present with AST OR ALT values $\geq 3 \times$ ULN AND a T bili value $\geq 2 \times$ ULN with no evidence of hemolysis and an alkaline phosphatase value $<2 \times$ ULN or not available (refer to Section 5.1 for guidance on when to discontinue the participant).
- For participants with baseline AST OR ALT OR T bili values above the ULN, the following threshold values are used in the definition mentioned above, as needed, depending on which values are above the ULN at baseline:

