 - Preexisting AST or ALT baseline values above the normal range: AST or ALT values ≥ 2 times the baseline values AND $\geq 3 \times$ ULN; or $\geq 8 \times$ ULN (whichever is smaller).
 - Preexisting values of T bili above the normal range: T bili level increased from baseline value by an amount of $\geq 1 \times$ ULN or if the value reaches $\geq 3 \times$ ULN (whichever is smaller).

Rises in AST/ALT and T bili separated by more than a few weeks should be assessed individually based on clinical judgment; any case where uncertainty remains as to whether it represents a potential Hy’s law case should be reviewed with the sponsor.

The participant should return to the investigator site and be evaluated as soon as possible, preferably within 48 hours from awareness of the abnormal results. This evaluation should include laboratory tests, detailed history, and physical assessment.

In addition to repeating measurements of AST and ALT and T bili for suspected Hy's law cases, additional laboratory tests should include albumin, CK, direct and indirect bilirubin, GGT, PT/INR, total bile acids, and alkaline phosphatase. Consideration should also be given to drawing a separate tube of clotted blood and an anticoagulated tube of blood for further testing, as needed, for further contemporaneous analyses at the time of the recognized initial abnormalities to determine etiology. A detailed history, including relevant information, such as review of ethanol, acetaminophen/paracetamol (either by itself or as a coformulated product in prescription or over-the-counter medications), recreational drug, or supplement (herbal) use and consumption, family history, sexual history, travel history, history of contact with a jaundiced person, surgery, blood transfusion, history of liver or allergic disease, and potential occupational exposure to chemicals, should be collected. Further testing for acute hepatitis A, B, C, D, and E infection, liver imaging (eg, biliary tract), and collection of serum samples for acetaminophen/paracetamol drug and/or protein adduct levels may be warranted.

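### The eDISH plots pair each enzyme peak only with same-day bilirubin, so a later bilirubin rise is plotted outside the Hy's law quadrant and, in the rare staggered case, has no joint display; QTcF > 500 ms also has no row of its own

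*SAP*

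**What the plan says.** **Liver plots.** SAP 18.3.1 plans four eDISH plots (AST, ALT, GGT, ALP), all of one form, for example "Maximum alanine aminotransferase (ALT) versus same-day total bilirubin". The version adjusted for elevated baseline changes only the scale. The rule for a maximum reached on two dates picks the date with the higher accompanying bilirubin, so it too stays with same-day pairs.

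**Combined liver row.** Under a heading that makes the hepatic rows by visit, the same section counts participants with > 3 × "ULN elevation in either ALT or AST and > 2 × ULN elevation in total bilirubin". It does not say whether both values must come from one sample. Elsewhere the section does set timing: the symptom row has a rule, "where temporal association is defined as ±14 days of onset date from the time of elevation", and low lymphocyte and neutrophil counts are tabulated "at end of treatment and anytime in the study".

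**Protocol on timing.** Appendix 6 states: "In the majority of DILI cases, elevations in AST and/or ALT precede T bili elevations", by several days or weeks. It adds that the bilirubin rise typically comes while AST/ALT is still above 3 × ULN, so that both are raised in the same sample. It then says: "In rare instances, by the time T bili elevations are detected, AST/ALT values might have decreased". Of that case it says: "This occurrence is still regarded as a potential DILI".

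**ECG.** SAP 18.4.1 has one absolute QTcF category (≥ 450 ms in men, ≥ 470 ms in women), puts its > 500 ms category on uncorrected QT, and has > 30 ms and > 60 ms change categories for both QT and QTcF. Protocol 9.9.3 calls for a repeat ECG at a new-onset QTc above 500 ms.

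**The concern.** An eDISH plot exists to show at a glance whether anyone had both a marked enzyme rise and a marked bilirubin rise. If enzymes usually peak first, the bilirubin value from the day of the enzyme peak is often the wrong one to plot: it was taken before bilirubin had risen. The plot can then show an empty Hy's law quadrant although a participant met both limits within a few weeks. The by-visit row is the back-up, but it cannot join rises that fall in different visit windows.

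For QT, a reader who wants to know how many participants passed the QTc level named in the protocol cannot take that number from the planned table.

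**Working it through.** The plan gives no figure to reproduce here, so I applied its display rules to illustrative participants. The laboratory values are assumptions, in multiples of ULN. AST is assumed to follow ALT. The SAP gives no reference lines for the plot, so I take the Hy's law quadrant as > 3 × enzyme and > 2 × bilirubin, as in the combined row.

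**Visit windows** (SAP Table 2): Week 2 = Days 2–22, Week 4 = Days 23–43, Week 8 = Days 44–71.

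**Rules applied**
- eDISH: (maximum ALT, bilirubin on that day)
- By-visit row: ALT > 3 × and bilirubin > 2 × within one visit
- Any-time row (proposed): each limit exceeded at some post-baseline time

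| Case | Week 4 (Day 29) ALT / bilirubin | Week 8 (Day 57) ALT / bilirubin | eDISH point | Peak against peak | By-visit row | Any-time row |
|---|---|---|---|---|---|---|
| A: ALT has fallen | 6.0 / 1.0 | 2.5 / 2.6 | (6.0, 1.0) | (6.0, 2.6) | 0 | 1 |
| B: ALT still raised | 6.0 / 1.0 | 4.0 / 2.6 | (6.0, 1.0) | (6.0, 2.6) | 1 (Week 8) | 1 |
| C: same day | 6.0 / 2.6 | 2.5 / 1.6 | (6.0, 2.6) | (6.0, 2.6) | 1 (Week 4) | 1 |

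Case B is the sequence that the protocol calls typical: the plot misses it and the combined row catches it. Case A is the rare sequence: both miss it. The gap in case A is 57 − 29 = 28 days, but a shorter one suffices. With ALT 6 × and bilirubin 1.0 × on Day 15, then 1.8 × and 2.4 × on Day 29 (29 − 15 = 14 days, Week 2 and Week 4 windows), the plot shows (6, 1.0), the by-visit row counts 0 and an any-time row counts 1.

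**Sample matching within one window.** Take Day 29 with ALT 6 × and bilirubin 1.1 ×, and Day 36 with ALT 2.5 × and bilirubin 2.6 ×, both in the Week 4 window. The by-visit row counts 1 if the rises may come from different samples in the window, and 0 if they must share a sample. SAP 6.3 says that all measurements enter summaries of abnormalities, which answers which samples are looked at but not whether they must match.

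**QT.** Fridericia: QTcF = QT / RR^(1/3), with RR = 60 / heart rate.
- QT 500 ms is QTcF 470.5 ms at 50 bpm and 526.4 ms at 70 bpm.
- QTcF 501 ms is QT 532.4 ms at 50 bpm, 501.0 at 60, 487.8 at 65, 465.1 at 75 and 422.6 at 100.

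Of the rates tested (50 to 100 bpm), the > 500 ms QT row misses a QTcF of 501 ms at 65 bpm and above. At 50 bpm it counts a QT of 501 ms, which is a QTcF of only 471.5 ms. It cannot stand in for a QTcF count.

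Protocol 9.4.1 excludes a pre-randomization QTcF of ≥ 450 ms (men) or ≥ 470 ms (women). Passing 500 ms therefore needs a rise of more than 500 − 450 = 50 ms or 500 − 470 = 30 ms. Every such value is thus already inside the ≥ 450/470 ms row and the > 30 ms change row, but is not separated there.

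**The case against.** The strongest reply is that nothing is lost. All laboratory results are listed in time order with out-of-range values flagged, the single-analyte rows show each rise, Appendix 6 requires potential Hy's law cases to be reported as SAEs, and SAP 18.1.5 adds a data review to find liver events that investigators missed. In a small study that stops early and plans no statistical comparison of safety data, listings carry much of the weight. All of this stands, and it is why the point is minor.

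Same-day pairing is also a legitimate choice. Protocol 10.12.2 asks only that related laboratory parameters be presented together, and peak against peak can join unrelated rises, the more so as participants with Gilbert's syndrome may enter. That stands as a reason to add a second version rather than replace the first. Appendix 6 already provides the follow-up, since rises "separated by more than a few weeks should be assessed individually based on clinical judgment".

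Four stronger readings are tempting but not supported:
- *The combined row has no timing rule.* Its heading makes it by visit. That restriction is what drops case A; a row with no timing limit would count it.
- *The usual DILI case goes unseen.* Appendix 6 says both values are typically raised in one sample, and the combined row counts that. Only the case called rare escapes both displays.
- *The choice of samples for the combined row is wide open.* SAP 6.4 would pick the result closest to schedule, but SAP 6.3 favours all measurements for abnormality counts. What stays open is the same-sample question.
- *The SAP contradicts the protocol on QT.* The protocol asks for outlier ECG results to be tabulated and sets no analysis category. This is a missing row, and the ECG listing shows the values.

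**Conclusion.** The point holds as a minor matter of display. The eDISH plots can misplace even the typical sequence. The by-visit row makes good the typical sequence but not a bilirubin rise at a later visit after ALT/AST has fallen to 3 × ULN or below, which then has no joint display. QTcF > 500 ms is counted only within broader categories. How many participants this affects cannot be derived from the documents. Few are to be expected, with 96 planned and enrolment stopping short of that. The case results rest on assumed laboratory values; the display rules are the SAP's own. Participant protection is not affected.

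**What to change.** Keep all existing outputs and add three items:
1. SAP 18.3.1: an eDISH version of peak post-baseline ALT (and AST) against peak post-baseline total bilirubin, with participants whose rises are separated in time flagged for case review as in Appendix 6.
2. SAP 18.3.1: a participant-level row for > 3 × ULN ALT/AST with > 2 × ULN bilirubin at any time post-baseline, in the manner already used for lymphocytes and neutrophils.
3. SAP 18.4.1: a > 500 ms category in QTcF.

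Two wording points can be settled at the same time. State whether the by-visit combined rows need both values from one sample. Reconcile SAP 18.3, which bars local results from summaries (except lipid and thyroid tests) and from maxima, with the 18.3.1 rule that central bilirubin takes precedence over local in the eDISH plot, which implies that local bilirubin can enter it.

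The cost is SAP wording, one added plot definition and two table rows, all on data already collected. The downside is that peak against peak may pair unrelated rises, which then need case review. If only central results are used, a bilirubin rise seen only locally stays in the listing.

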#### 18.3.2. Pregnancy Tests

Urine beta-human chorionic gonadotropin ( $\beta$ -hCG) and/or serum  $\beta$ -hCG pregnancy tests are performed throughout the study in female participants of childbearing potential. All pregnancy test results (positive or negative) will be listed in chronological order.

#### 18.3.3. Other Screening Laboratory Assessments

Screening laboratory assessments for virology, drug screen/toxicology, QuantiFERON Tuberculosis (TB) Gold, stool pathogens, and Clostridioides difficile (formerly known as Clostridium difficile) will be listed. Analyses of exploratory efficacy-related biomarkers data based on samples collected at Screening in participants who provided consent will be described in a separate plan.

#### 18.4. ECG Evaluations

Electrocardiograms (ECG) are recorded on a 12-lead ECG machine and read centrally. The following ECG parameters will be reported for this study:

- HR (beats per minute [bpm])
- PR interval (ms)
- RR interval (ms)
- QRS interval (ms)
- QT interval (ms)
- QTcF interval (ms)
- Overall interpretation of ECG (Investigator's judgment):
  - Normal
  - Abnormal, Not Clinically Significant (Abnormal not clinically significant [NCS])
  - Abnormal, Clinically Significant (Abnormal CS)
- Overall interpretation of ECG (central reader):
  - Normal

Document: \quintiles.net\enterprise\Apps\sasdata\SASb\SAS\Arena\APD334\RZA28116\Biostatistics\Documenta

tion\SAP\503-Final SAP v2.0\APD334-203\_SAP\_Final v2.0-20231120\_clean.docx

Author: PPD Version Number: 2.0

Version Date: 20Nov2023

Template No.: CS\_TP\_BS016 Revision 7 Reference: CS\_WI\_BS005

Effective Date: 01Nov2021

Page 47 of 70

- Abnormal NCS
- Abnormal CS
- AV conduction abnormalities
  - First degree AV block
  - Second degree AV block type 1
  - Second degree AV block type 2
  - Third-degree AV block

The following summaries will be provided for ECG data:

- Value and change from Baseline by visit (for quantitative measurements)
- Incidence of markedly abnormal values (defined in Section 18.4.1) and AV blocks by visit
- Shift in normal/abnormal NCS/abnormal CS in the overall interpretation (by investigator) from Baseline to end
  of treatment and to the worst-case post-Baseline
- Shift in markedly abnormal categories from Baseline to post-Baseline by visit

Listings of ECG results, including first dose cardiac monitoring, and discharge criteria for first dose cardiac monitoring will be provided.

A listing of all ECG assessments over time in participants meeting markedly abnormal criteria will also be provided. For each subject, only ECG parameters ever meeting markedly abnormal criteria will be included.

#### 18.4.1. ECG Markedly Abnormal Criteria

Markedly abnormal quantitative ECG measurements will be identified in accordance with the following predefined markedly abnormal criteria:

- Absolute values in QT and QTcF:
  - ≥ 450 ms (male) or ≥ 470 ms (female) in QTcF
  - > 500 ms in QT
- Change from Baseline in QT and QTcF:
  - > 30 ms increase from Baseline
  - > 60 ms increase from Baseline

Document: \quintiles.net\enterprise\Apps\sasdata\SASb\SAS\Arena\APD334\RZA28116\Biostatistics\Documenta

tion\SAP\503-Final SAP v2.0\APD334-203\_SAP\_Final v2.0-20231120\_clean.docx

Author: PPD Version Number: 2.0

Version Date: 20Nov2023

Template No.: CS\_TP\_BS016 Revision 7 Reference: CS\_WI\_BS005

Effective Date: 01Nov2021

Page 48 of 70

In shift tables, participants will be classified according to the binary category for each parameter and the predefined markedly abnormal criterion (ie, Markedly abnormal versus Not markedly abnormal, with Markedly abnormal defined in the footnote).

